2.3.4 Benefit and risk assessment in the context of COVID-19 pandemic

[figure not shown]
Please refer to the master protocol for more details about risks related to the patient population, SAR444245 treatment, and study related activity.

In addition, the impact of PD-1 blockade therapy on Coronavirus disease 2019 (COVID-19) severity was also explored by 2 groups and did not find a clinically meaningful signal (33, 34).

3 OBJECTIVES AND ENDPOINTS

Please refer to the master protocol for description of common objectives and endpoints. Substudy-specific objectives and endpoints are summarized below.

Table 2 - Objectives and endpoints

Objectives	Endpoints
Secondary 
• To assess active concentrations of cetuximab when given in combination with SAR444245• C_{trough} and $C_{\text{end of infusion}}$ of cetuximab	
Exploratory 	

3.1 APPROPRIATENESS OF MEASUREMENTS

Please refer to the master protocol.

4 STUDY DESIGN

4.1 OVERALL DESIGN

Cohorts D1 and D2 will assess SAR444245 adding on to either pembrolizumab or cetuximab, respectively, in participants with advanced unresectable or metastatic colorectal cancer (mCRC) who have progressed on prior regimens having contained fluoropyrimidine, oxaliplatin, irinotecan, with either bevacizumab or cetuximab, and with no more than 5 prior lines of treatments. Patients are not eligible if MSI-H. Patients with *RASmut* are not eligible for enrollment in Cohort D2.

Please refer to the master protocol for a full description of the study design, and for details applicable to all therapy cohorts.

A graphical presentation of the substudy schema is shown in [Figure 1](#). For treatment period, the completion of Cycle 35 is only applicable for Cohort D1.

4.2 SCIENTIFIC RATIONALE FOR STUDY DESIGN

The proposed substudy aims to establish proof-of-concept that combining the non-alpha-IL2 SAR444245 with either the anti-PD1 antibody pembrolizumab or with the anti-EGFR IgG1 antibody cetuximab will result in a significant increase in the population experiencing an objective response.

The design of the study is a non-randomized study where the experimental combination will be assessed in a single cohort for each indication, using historical data for single agent immune-checkpoint, or anti-EGFR therapy as a benchmark to show outstanding objective response rate. The ORR will be assessed using RECIST 1.1 for participants with advanced and metastatic colorectal cancer.

Please refer to the master protocol for more information.

4.2.1 Participant input into design

There was no participant input into design of the trial.

4.3 JUSTIFICATION FOR DOSE

4.3.1 SAR444245 dose

Please refer to the master protocol.

4.3.2 Pembrolizumab dose

The planned dose of pembrolizumab for this study is 200 mg every 3 weeks (Q3W). Based on the totality of data generated in the Keytruda development program, 200 mg Q3W is an appropriate dose of pembrolizumab for adults across all indications. As outlined below, this dose is justified by:

- Clinical data from 8 randomized studies in melanoma and NSCLC indications demonstrating flat dose- and exposure-efficacy relationships from 2 mg/kg Q3W to 10 mg/kg every 2 weeks (Q2W) representing an approximate 5 to 7.5 fold exposure range (refer to the pembrolizumab IB).
- Population PK analysis showing that both fixed dosing and weight-based dosing provides similar control of PK variability with considerable overlap in the distributions of exposures, supporting suitability of 200 mg Q3W
- Clinical data showing meaningful improvement in benefit-risk including overall survival at 200 mg Q3W across multiple indications. And
- Pharmacology data showing full target saturation in both systemic circulation (inferred from PK data) and tumor (inferred from physiologically-based PK [PBPK] analysis) at 200 mg Q3W.

Among the 8 randomized dose-comparison studies, a total of 2262 participants were enrolled with melanoma and NSCLC, covering different disease settings (treatment naïve, previously treated, PD-L1 enriched, and all-comers) and different treatment settings (monotherapy and in combination with chemotherapy). Five studies compared 2 mg/kg Q3W versus 10 mg/kg Q2W (KN001 Cohort B2, KN001 Cohort D, KN002, KN010, and KN021), and 3 studies compared 10 mg/kg Q3W versus 10 mg/kg Q2W (KN001 Cohort B3, KN001 Cohort F2 and KN006). All of these studies demonstrated flat dose- and exposure-response relationships across the doses studied representing an approximate 5- to 7.5- fold difference in exposure. The 2 mg/kg (or 200 mg fixed-dose) Q3W provided similar responses to the highest doses studied. Subsequently, flat dose-exposure-response relationships were also observed in other tumor types including head and neck cancer, bladder cancer, gastric cancer and classical Hodgkin Lymphoma, confirming 200 mg Q3W as the appropriate dose independent of the tumor type. These findings are consistent with the mechanism of action of pembrolizumab, which acts by interaction with immune cells, and not via direct binding to cancer cells.

Additionally, pharmacology data clearly show target saturation at 200 mg Q3W. First, PK data in KN001 evaluating target-mediated drug disposition (TMDD) conclusively demonstrated saturation of PD1 in systemic circulation at doses much lower than 200 mg Q3W. Second, a PBPK analysis was conducted to predict tumor PD1 saturation over a wide range of tumor penetration and PD1 expression. This evaluation concluded that pembrolizumab at 200 mg Q3W achieves full PD1 saturation in both blood and tumor.

Finally, population PK analysis of pembrolizumab, which characterized the influence of body weight and other participant covariates on exposure, has shown that the fixed-dosing provides similar control of PK variability as weight-based dosing, with considerable overlap in the distribution of exposures from the 200 mg Q3W fixed dose and 2 mg/kg Q3W dose. Supported by

these PK characteristics and given that fixed-dose has advantages of reduced dosing complexity and reduced potential of dosing errors, the 200 mg Q3W fixed-dose was selected for evaluation across all pembrolizumab protocols.

4.3.3 Cetuximab dose

This study proposes to evaluate the clinical benefit of 24 $\mu\text{g}/\text{kg}$ SAR444245 Q3W combined with the approved dose of 400 mg/m^2 cetuximab as an IV infusion on day 1 of the study followed by subsequent doses of 250 mg/m^2 cetuximab IV QW.

4.4 END OF STUDY DEFINITION

Please refer to the master protocol.

5 STUDY POPULATION

See the master protocol for a full list of common inclusion and exclusion criteria and the subsections below for Cohorts D1 and D2 specific criteria.

5.1 INCLUSION CRITERIA

Participants are eligible to be included in the study only if all of the following criteria apply (in addition to the criteria listed presented in the master protocol):

Type of participant and disease characteristics

- I 01. Histologically or cytologically confirmed diagnosis of colorectal cancer. Only patients with non-MSI-H disease are eligible.
- I 02. Confirmed diagnosis at study entry of advanced unresectable or metastatic disease.

Note: *For participants in Cohort D1 and D2*: Disease with any CPS scoring. No need for CPS determination at local laboratory.
- I 03. **MSI status:** Participants must have MSI status known or determined locally and must have non-MSI-H disease to be eligible. **Other genetic aberrations:** Participants in Cohort D2 must have *RAS* wild-type disease.
- I 04. **Prior anticancer therapy:** Participants should have failed or relapsed on at least 2 but no more than 5 prior regimens having contained fluoropyrimidine, oxaliplatin, irinotecan, with bevacizumab and/or cetuximab.
- I 05. **Provision of tumor tissue:**
 - **Mandatory baseline biopsy** for participants in **Cohorts D1, and D2**: minimum 5 slides with 4-5 micron thickness for the first 20 participants who have signed ICF (excluding screen failure participants), minimum 10 slides with 4-5 micron thickness for subsequent participants in each cohort. Archival tumor tissue samples should be obtained from biopsies done within 6 months, and there should be no systemic anti-cancer therapy between collection of biopsy and enrollment. Slides specifications are detailed in Lab Manual.
 - **Mandatory on-treatment biopsy** for at least 20 participants in each of **Cohort D1 and Cohort D2**, if clinically feasible. On-treatment biopsies are otherwise **optional** per Investigator's discretion and evaluation of all other participants.
 - The Sponsor may approve the written request to enroll, on a case-by-case basis, participants with:
 - location of the tumor not amenable to biopsy due to significant risk, OR
 - less than required number of slides or archival tumor tissue sample collected more than 6 months prior to enrollment.

5.2 EXCLUSION CRITERIA

Participants are excluded from the study if any of the following criteria apply (in addition to the criteria listed in the master protocol):

Medical conditions

E 01. Electrolyte (magnesium, calcium, potassium) levels outside of normal ranges for participants in Cohort D2.

Prior/concomitant therapy

E 02. *For participants in Cohort D1.* - Prior treatment with an agent (approved or investigational) that blocks the PD-1/PD-L1 pathway (participants who joined a study with an anti-PD-1/PD-L1 but have written confirmation they were on control arm are allowed).

5.3 LIFESTYLE CONSIDERATIONS

Please refer to the master protocol.

5.4 SCREEN FAILURES

Please refer to the master protocol.

5.5 CRITERIA FOR TEMPORARILY DELAYING ENROLLMENT/RANDOMIZATION/ADMINISTRATION OF STUDY INTERVENTION

Please refer to the master protocol.

6 STUDY INTERVENTION(S) AND CONCOMITANT THERAPY

6.1 STUDY INTERVENTION(S) ADMINISTERED

Please refer to the master protocol.

For study treatment duration, completion of Cycle 35 is only applicable for Cohort D1.

Dosing sequence for Cohort D1: [REDACTED]

Enrolled participants in Cohort D2 will receive treatment with both SAR444245 and cetuximab until PD.

Dosing sequence for Cohort D2: [REDACTED]

In addition, if a participant has immune unconfirmed progression of disease (iUPD) and is clinically stable, it is at the discretion of the Investigator to continue treating the subject with the assigned treatment per protocol until progression of disease is confirmed (iCPD) at least 4 weeks, but no longer than 8 weeks from the date of the scan suggesting progression of disease (Section 10.9).

6.1.1 Investigational medicinal product (IMP)

Investigation medicinal product is defined as SAR444245, pembrolizumab, and cetuximab administered in combination as described in Section 4. Details of each IMP component to be administered are shown in Table 3.

Preparation and administration of IMP are detailed in the pharmacy manual.

Hydration is required for SAR444245 infusions. Details are provided in Section 6.1.3 of the master protocol.

Table 3 - Overview of IMP administered

Intervention name	SAR444245	Pembrolizumab	Cetuximab
Type	See master protocol	Biologic	Biologic
Dose formulation	See master protocol	Solution for infusion	Solution for injection
Unit dose strength(s)	See master protocol	100 mg/vial	As per locally approved formulation
Dosage level(s)^a	24 µg/kg Q3W	200 mg Q3W	An initial loading dose of 400 mg/m ² on C1D1, followed by 250 mg/m ² once weekly
Route of administration	See master protocol	IV infusion	IV infusion
Use	See master protocol	Treatment of cancer (combination)	Treatment of cancer (combination)
IMP or NIMP	See master protocol	IMP	IMP
Packaging and labeling	See master protocol	Supplied in single dose vials containing 100 mg/4 mL pembrolizumab labelled with a multilingual booklet. 1 vial per treatment box.	To be locally sourced as locally available/marketed where possible. Central sourcing (EU sourced and clinically labeled only for the countries where local sourcing is not possible)
Current/Former name(s) or alias(es)	See master protocol	Keytruda	As per locally approved formulation

a See master protocol.

6.1.2 Non-investigational medicinal products

Non-investigational medicinal products include the premedication administered for SAR444245 and cetuximab.

For Cohort D1, in case of permanent SAR444245 discontinuation and continuation of pembrolizumab treatment as part of AE management, SAR444245 premedication no longer needs to be administered.

6.1.2.1 *Premedication for SAR444245*

Please refer to the master protocol.

6.1.2.2 *Premedication for cetuximab*

All participants who will receive cetuximab should be premedicated with diphenhydramine 25 to 50 mg IV (or equivalent) prior to the first dose of cetuximab or any other recommended premedication as per local requirements. Premedication for subsequent doses of cetuximab should be given per medical judgment and history of prior infusion reactions (IRs).

[REDACTED]

When SAR444245 and cetuximab are given on the same day, participants who have received diphenhydramine as cetuximab premedication may skip the diphenhydramine as SAR444245 premedication.

6.1.3 Hydration guidelines for SAR444245 administration

Please refer to the master protocol.

6.1.4 Readiness for treatment of severe cytokine release syndrome

Please refer to the master protocol.

6.2 PREPARATION/HANDLING/STORAGE/ACCOUNTABILITY

Please refer to the master protocol.

6.3 MEASURES TO MINIMIZE BIAS: RANDOMIZATION AND BLINDING

Not applicable.

6.4 STUDY INTERVENTION COMPLIANCE

Please refer to the master protocol.

6.5 DOSE MODIFICATION

6.5.1 General rules

Dose modifications for SAR444245 and cetuximab are permitted, according to the guidelines described in this section. Pembrolizumab dose reductions are not permitted. Pembrolizumab treatment may be interrupted or discontinued due to toxicity.

Dose modifications different from those stated in the protocol should only be made in consultation with the Sponsor, unless required for immediate participant safety.

Cycle delay (ie, Day 1 should be delayed for all IMPs) is permitted in case of treatment-emergent adverse event (TEAE). Dose modification will be made according to the worst grade of toxicity observed within a cycle. If a participant experiences several toxicities and there are conflicting recommendations, the most conservative recommended dose adjustment should be followed.

In participants who have SAR444245 dose reduction due to SAR444245 related Grade ≥ 3 treatment-related adverse events (TRAEs), SAR444245 dose may be re-escalated to █ µg/kg if:

- no SAR444245 related Grade ≥ 3 TRAE or clinically significant laboratory abnormality within at least 2 subsequent cycles, AND
- both Investigator and Sponsor agree that the participant has clinical benefit.

Administration of the study treatment will be discontinued in the event of a TEAE that persists despite appropriate dose modifications or any other TEAE that, in the opinion of the Investigator, warrants discontinuation.

If any of the IMP components is permanently discontinued, the other IMP component can be continued until disease progression or other criteria as detailed in Section 7.1.1 of the master protocol are met. In this case, it is partial permanent discontinuation, and the end of treatment (EOT) assessment will be 30 days after the date of the last administration of the remaining IMP. When all IMP components are permanently discontinued, it is full permanent discontinuation.

All changes to study treatment administration must be recorded in the electronic case report form (e-CRF).

6.5.2 Cycle delay

The treatment window is ± 3 days for each of the Q3W administrations. The treatment window is ± 1 day for cetuximab administration on Day 8 and Day 15 of each cycle.

A cycle is deemed to have been delayed if the treatment is administered ≥ 4 days beyond the theoretical day of Q3W IMP administration. The participant may receive the next dose after recovery from the toxicity as described in [Section 6.5.3](#) and [Section 6.5.4](#). After cycle is delayed, such participants may be considered for treatment resumption once the toxicity resolves or improves to Grade 1 or baseline.

Participants may have cycle delay, if toxicity occurs and the participant does not recover according to following rules:

- For Q3W IMP administration: If toxicity occurs and the participant does not recover on the day of planned administration, the cycle will be delayed; restart of study IMPs could occur only on the initiation of the subsequent cycle.
- For cetuximab Day 8 and Day 15 administration in each cycle: if toxicity occurs and the patient does not recover on the day of planned infusion or within the following 3 days, infusion may be omitted.
- In case of cycle delay or dose omissions for the recovery of toxicity, the following rules should be followed for restart or discontinuation of the treatment:
 - In case of a cycle delay up to 14 days or a dose omission, it is per Investigator's decision to restart the study treatment.
 - After a cycle delay of >14 days and ≤ 84 days, or 2 to 4 consecutive dose omissions, it is per Investigator's decision to restart the study treatment or the IMP that is omitted, if a clear benefit from treatment is observed and after consultation with the Sponsor.
 - The study treatment must be permanently discontinued if the cycle delay is longer than 84 days, or if the participant has more than 4 consecutive dose omissions.
 - For any delayed cetuximab treatment, do not repeat the initial dose of 400 mg/m^2 . At the restart of cetuximab treatment, all subsequent infusions will be at the appropriate dose level according to [Table 4](#).
- Cycle delay or dose omission may be considered for situations other than TEAEs such as medical/surgical events or logistical reasons not related to study therapy. Participants should be placed back on study therapy within 21 days of the scheduled delay or omission, unless otherwise discussed with the Sponsor (for example for national or regional emergencies). The reason for the delay or omission should be documented in the participant's study record.

Modification of dose levels in case of dose reduction

Dose reduction steps for cetuximab are shown in [Table 4](#). One or several doses of cetuximab can be omitted.

Table 4 - Dose levels for cetuximab dose reduction

Starting dose	Dose level 1	Dose level 2
400 mg/m ² then	200 mg/m ²	150 mg/m ²
250 mg/m ²	(20% decrease)	(20% decrease)

6.5.3 General guidelines for the management of treatment-related adverse events

Participants who experience Grade ≥ 3 TRAEs at any time of the study (including clinically significant Grade 3 laboratory abnormalities as defined in Section 10.3.1 of the master protocol) not listed in [Section 6.5.4](#) (Tables 5-11) will be required to temporarily cycle delay the IMP. After cycle delay, such participants may be considered for treatment resumption once the TRAE resolves or improves to Grade 1 or baseline.

The dose of SAR444245 should be reduced to █ μg/kg (with the exception of lymphocytopenia which is directly associated with SAR444245 mode-of-action and does not require dose reduction) in cases of:

- First occurrence of Grade 3 TRAE that does not resolve to Grade 1 or baseline within 72 hours, and second occurrence of Grade 3 TRAE of any duration.
- Grade 4 TRAE.
- First occurrence of Grade 3 laboratory abnormality that are clinically significant per Section 10.3.1 of the master protocol. and that do not resolve to Grade 1 or baseline within 72 hours, and second occurrence of Grade 3 clinically significant laboratory abnormality of any duration.
- Grade 4 laboratory abnormalities that are clinically significant.

Treatment resumption is at the discretion of the Investigator and Sponsor, if thought to be in the best interest of the participant, except when specified otherwise in this protocol, or if the event has required the IMP temporary interruption for more than 84 days from the last scheduled dose.

The cycle delay of treatment for Grade 2 events is left at the discretion of the Investigator unless otherwise specified in this protocol.

No cycle delay of treatment or dose modification is required for Grade 1 events.

The final decision on dose modification and/or corrective therapy will be based on the Investigator's judgment, in the best interest of the participant.

Recommended guidelines for the management of specific adverse events including irAE, CRS, Vascular Leak Syndrome (VLS) and Infusion-related reactions (IRR) are presented in [Section 6.5.4](#).

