6.5.3 General guidelines for the management of treatment-related adverse events

Participants who experience Grade ≥ 3 TRAEs at any time of the study (including clinically significant Grade 3 laboratory abnormalities as defined in Section 10.3.1 of the master protocol) not listed in [Section 6.5.4](#) (Tables 3-8) will be required to temporarily delay the IMP. After cycle delay, such participants may be considered for treatment resumption once the TRAE resolves or improves to Grade 1 or baseline.

The dose of SAR444245 should be reduced to █ µg/kg (with the exception of lymphocytopenia which is directly associated with SAR444245 mode-of-action and does not require dose reduction) in cases of:

- First occurrence of Grade 3 TRAE that does not resolve to Grade 1 or baseline within 72 hours, and second occurrence of Grade 3 TRAE of any duration.
- Grade 4 TRAE.
- First occurrence of Grade 3 laboratory abnormality that are clinically significant per Section 10.3.1 of the master protocol. and that do not resolve to Grade 1 or baseline within 72 hours, and second occurrence of Grade 3 clinically significant laboratory abnormality of any duration.
- Grade 4 laboratory abnormalities that are clinically significant.

Treatment resumption is at the discretion of the Investigator and Sponsor, if thought to be in the best interest of the participant, except when specified otherwise in this protocol, or if the event has required the IMP temporary interruption for more than 84 days from the last scheduled dose.

The cycle delay of treatment for Grade 2 events is left at the discretion of the Investigator unless otherwise specified in this protocol.

No cycle delay of treatment or dose modification is required for Grade 1 events.

The final decision on dose modification and/or corrective therapy will be based on the Investigator's judgment, in the best interest of the participant.

Recommended guidelines for the management of specific adverse events including irAE, CRS, Vascular Leak Syndrome (VLS) and Infusion-related reactions (IRR) are presented in [Section 6.5.4](#).

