Cetuximab can cause dermatologic toxicities, including acneiform rash, skin drying and fissuring, paronychial inflammation, infectious sequelae (for example, *S. aureus* sepsis, abscess formation, cellulitis, blepharitis, conjunctivitis, keratitis/ulcerative keratitis with decreased visual acuity, cheilitis), and hypertrichosis. Acneiform rash occurred in 82% of patients across clinical trials. Grades 3 or 4 acneiform rash occurred in 9.7% of patients. Acneiform rash usually developed within the first two weeks of therapy; the rash lasted more than 28 days after stopping treatment in

most patients. Life-threatening and fatal bullous mucocutaneous disease with blisters, erosions, and skin sloughing, has been observed. It could not be determined whether these mucocutaneous adverse reactions were directly related to EGFR inhibition or to idiosyncratic immune-related effects (eg, Stevens-Johnson syndrome or toxic epidermal necrolysis).

Cetuximab can cause hypomagnesemia which occurred in 55% patients in various clinical trials, including Grades 3 and 4 in 6% to 17%. Hypomagnesemia and accompanying electrolyte abnormalities can occur days to months after initiating treatment. It is recommended to monitor patients weekly during treatment for hypomagnesemia, hypocalcemia, and hypokalemia, and for at least 8 weeks following the completion of treatment and to replete electrolytes as necessary.

Based on animal data and its mechanism of action, cetuximab can cause fetal harm when administered to a pregnant woman. There are no available data for cetuximab exposure in pregnant women. In an animal reproduction study, intravenous administration of cetuximab once weekly to pregnant cynomolgus monkeys resulted in an increased incidence of embryo-lethality and abortion. Disruption or depletion of EGFR in animal models results in impairment of embryo-fetal development including effects on placental, lung, cardiac, skin, and neural development.

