6.5.4.7 Dermatologic toxicity

Cetuximab can cause dermatologic toxicities, including acneiform rash, skin drying and fissuring, paronychial inflammation, infectious sequelae (for example, *S. aureus* sepsis, abscess formation, cellulitis, blepharitis, conjunctivitis, keratitis/ulcerative keratitis with decreased visual acuity, cheilitis), and hypertrichosis.

The dosing of cetuximab will be omitted 1 to 2 weeks in the case of severe (Grade 3 or 4) acneiform rash. If acneiform rash improves during this time, then the dose of cetuximab should be reduced as indicated in [Table 12](#). The dose modification guidelines as per the current local label should be followed for dermatologic toxicities other than acneiform rash.

If acneiform rash does not improve during this time, cetuximab will be permanently discontinued.

Participant who have held cetuximab therapy for more than 2 consecutive infusions due to acneiform rash, and upon resolution of the toxicity are still felt to be benefiting from cetuximab treatment may resume cetuximab with Sponsor approval.

Table 12 - Cetuximab dose modification for dermatologic toxicities

Dermatologic toxicities and infectious sequelae (eg, acneiform rash, mucocutaneous disease)	Recommended cetuximab dose modification
1st occurrence; Grade 3 or 4	Day 1 of cycle: delay cycle until condition improves Within cycle: Omit infusion 1 to 2 weeks; if condition improves, continue at the same dose of 250 mg/m². If no improvement, discontinue cetuximab.
2nd occurrence; Grade 3 or 4	Day 1 of cycle: delay cycle until condition improves Within cycle: Omit infusion 1 to 2 weeks; if condition improves, permanently reduce at 200 mg/m ² . If no improvement, discontinue cetuximab.
3rd occurrence; Grade 3 or 4	Day 1 of cycle: delay cycle until condition improves Within cycle: Omit infusion 1 to 2 weeks; if condition improves, permanently reduce at 150 mg/m ² . If no improvement, discontinue cetuximab.
4th occurrence; Grade 3 or 4	Permanently discontinue cetuximab.

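### Substudy 04 gives conflicting instructions for a Grade 3-4 cetuximab rash: whether the general delay rule applies, whether a SAR444245 reduction needs attribution, and what happens to cetuximab after a first severe rash

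*Protocol*

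**What the plan says.** All references are to substudy 04 (Cohort D2, SAR444245 plus cetuximab) unless stated.

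- **Section 6.5.3, delay rule.** Grade 3 or higher treatment-related adverse events (TRAEs) that are not listed in Section 6.5.4 lead to a cycle delay. The exemption names Section 6.5.4 and then a table range: "Tables 5-11) will be required to temporarily cycle delay the IMP". Treatment may restart at Grade 1 or baseline.
- **Section 6.5.1, meaning of a delay.** "Cycle delay (ie, Day 1 should be delayed for all IMPs) is permitted in case of treatment-emergent adverse event (TEAE".
- **Section 6.5.3, SAR444245 reduction list.** It starts with "First occurrence of Grade 3 TRAE that does not resolve to Grade 1 or baseline within 72 hours" and goes on to a second Grade 3 TRAE of any duration, any Grade 4 TRAE, and clinically significant laboratory abnormalities on similar terms. Lymphocytopenia is the only exception. The section ends by leaving the final decision to the Investigator.
- **Section 6.5.1, re-escalation.** The provision opens "In participants who have SAR444245 dose reduction due to SAR444245 related Grade", so it covers only reductions made for events related to SAR444245.
- **Section 6.5.4.7, text.** Cetuximab is omitted for 1 to 2 weeks for a severe acneiform rash. "If acneiform rash improves during this time, then the dose of cetuximab should be reduced as indicated in" Table 12. Other dermatologic toxicities are referred to the local label.
- **Section 6.5.4.7, Table 12.** For a first Grade 3 or 4 occurrence within a cycle: "if condition improves, continue at the same dose of 250 mg/m²". The table's heading covers dermatologic toxicities and infectious sequelae, with mucocutaneous disease as an example beside rash. For an event on Day 1, the first three occurrence rows delay the cycle until the condition has improved.
- **Section 2.3.1.2.** "Grades 3 or 4 acneiform rash occurred in 9.7% of patients".

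**The concern.** A site facing a severe cetuximab rash must decide three things: whether to delay both drugs and when to restart, whether to lower SAR444245, and what to do with cetuximab. The protocol gives more than one answer to each.

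Severe rash is a known and fairly frequent effect of cetuximab, so the conflict is likely to be met in practice. If sites resolve it differently, exposure to SAR444245 and cetuximab in D2 will depend partly on local interpretation. D2 is an open-label, single-arm cohort whose response rate is read against historical data (Section 4.2), so it has no concurrent control to absorb such differences. These are also safety instructions, which should be unambiguous in their own right.

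**Working it through.** **1. Scope of the delay rule.** Read by section number, rash is exempt, because 6.5.4.7 is part of 6.5.4. Read by table range, it is not, because Table 12 falls outside Tables 5 to 11. The sentence supports both readings.

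**2. What the two readings change.** SAR444245 is given only on Day 1 of each cycle (Section 1.3).

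| Situation | Table 12 | General rule |
|---|---|---|
| Severe rash on Day 1 | Delay the cycle | Delay the cycle |
| Restart after the delay | Condition has improved | Grade 1 or baseline (6.5.3; the same in 6.5.2) |
| Severe rash within a cycle | Omit cetuximab for 1 to 2 weeks | Delay all IMPs |

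On Day 1 the difference is the restart criterion. A rash that has gone from Grade 3 to Grade 2 has improved, but it has not reached Grade 1 or baseline.

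**3. SAR444245 reduction.** The reduction paragraph has no table exemption of its own, so this step does not depend on how the range in step 1 is read. It refers to TRAEs without naming the responsible drug. Taken literally it covers a Grade 4 rash, a second Grade 3 rash, and a first Grade 3 rash that has not reached Grade 1 or baseline within 72 hours. It does not cover a first Grade 3 rash that reaches Grade 1 or baseline within 72 hours. Re-escalation in 6.5.1 is limited to reductions for SAR444245-related events, so a reduction for a cetuximab-only event has no stated way back. Attribution may itself be hard to settle, because Section 2.3.1.3 says SAR444245 could increase cetuximab's skin toxicity.

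**4. Section 6.5.4.7 against Table 12.** After a first severe rash improves, the text calls for a reduction as shown in the table, and the table's first row shows none. For dermatologic toxicities other than acneiform rash, the text points to the local label while the table's heading includes them.

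**5. How often this would arise.** Inputs: a rate of 9.7% (Section 2.3.1.2) and 40 participants (Section 9.2).

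- Check of the method on the protocol's own figures in Section 9.2: 1 − 0.99^40 = 33.1%, 1 − 0.98^40 = 55.4%, 1 − 0.95^40 = 87.1%. All three are reproduced.
- Expected Grade 3-4 rashes: 40 × 0.097 = 3.88, about 3.9.
- At least one: 1 − 0.903^40 = 98.3%.
- At least two: 1 − 0.903^40 − 40 × 0.097 × 0.903^39 = 91.1%.
- If the true rate were anywhere from 5% to 20% (an assumed range), 2 to 8 would be expected, and the chance of at least one would run from 87.1% to above 99.9%.

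**The case against.** The strongest reply is that this is loose cross-referencing in a section headed as general guidelines. The exemption names Section 6.5.4, Table 12 itself delays the cycle on Day 1, the reference in 6.5.1 to SAR444245-related events hints at the intended scope, and the Investigator decides in the end. The master protocol, which may define how TRAEs are attributed to each drug, is not shown. All of this stands, and it limits the point. It does not reconcile the instructions: discretion leaves a site to choose between them, and the mismatch between the 6.5.4.7 text and Table 12 remains on any reading.

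Four stronger readings are tempting and are not supported.

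- *That omitting Table 12 forces a SAR444245 reduction.* The table range sits in the delay sentence only. The reduction list carries no table exemption, so extending the range would not alter it. The missing attribution rule is a separate cause.
- *That a severe rash almost always outlasts 72 hours.* Section 2.3.1.2 says rash lasted more than 28 days after stopping treatment in most patients, but that is not limited to Grade 3-4. A rash that persists at Grade 1 meets the 72-hour condition. No time from Grade 3 to Grade 1 is given.
- *That 15% to 25% of D2 would have SAR444245 reduced.* This combines rash with Grade 3-4 hypomagnesaemia (6% to 17%): 1 − 0.903 × 0.94 = 15% and 1 − 0.903 × 0.83 = 25%. It assumes independence, that every event meets the trigger, that every laboratory event is clinically significant, and that no Investigator uses discretion. It is a ceiling.
- *That substudy 03 has the same conflict.* Its range, "Tables 3-8) will be required to temporarily delay the IMP", does leave out Table 9 on hepatic events. But 6.5.4.7 there already holds both drugs and describes this as a cycle delay, so no conflict over the delay is shown.

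A reader might also see a contradiction between stopping cetuximab when a rash has not improved in 1 to 2 weeks and allowing it to resume after more than two held infusions. The Day 1 delay in Table 12 has no such time limit and resumption needs Sponsor approval, so both can apply.

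**Conclusion.** The instructions for a Grade 3-4 cetuximab rash in substudy 04 are wrong as written, in three limited respects: an exemption whose section reference and table range disagree, with differing restart criteria; a SAR444245 reduction rule without the attribution wording that the re-escalation rule relies on; and a rash text that disagrees with Table 12 on the first occurrence and on scope.

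The conflict would very probably be met in D2: about 3.9 Grade 3-4 rashes expected among 40, and a 98% chance of at least one. That count takes the protocol's cross-trial rate as applying to D2 and treats participants as independent. It counts rashes, not dose reductions. The number who would have SAR444245 reduced, and any effect on the D2 response rate, cannot be derived from the documents.

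**What to change.** In the next amendment of substudy 04, the sponsor should reconcile Sections 6.5.1, 6.5.2, 6.5.3 and 6.5.4.7 so that:

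- the section reference and the table range in the 6.5.3 exemption cover the same events, and the restart criteria agree;
- 6.5.1 and 6.5.3 state the same rule on whether SAR444245 reduction requires attribution to SAR444245, and 6.5.1 says what follows for anyone reduced for another reason;
- the 6.5.4.7 text and Table 12 agree on the first severe occurrence and on which dermatologic toxicities the table governs.

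Which rule is clinically right is for the sponsor to decide; none is proposed here. The cost is a text correction and its communication to sites. Sample size, endpoints and analysis are unchanged.
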